9.2.1 Primary Outcome Analyses

The primary outcome of PrEP uptake is measured at the 3-month follow-up. The effectiveness of the intervention will be estimated as the difference in proportion of participants starting PrEP within 3 months of an index STI clinic visit, comparing patients randomized to the intervention and control groups. For participants enrolled through clinic-collaborating outreach events, the date of clinic outreach serves as the index visit.

9.2.2 Secondary Outcomes Analyses

Secondary effectiveness outcomes are listed in Table 3 (Section 7.0) including PrEP uptake at 6-months, and PrEP care engagement, PrEP use, PrEP adherence, incident STI/HIV, and PrEP stigma (at both 3- and 6-months, determined by when they are enrolled in the course of study enrollment). All analyses will follow the specifications described above in 9.2.

PrEP adherence at 3 and 6 months will be assessed using PrEP metabolite levels and self-report (3-month only for persons enrolled in approximately the final quarter of enrollment). We will use standard of care quarterly STI/HIV testing results to examine differential rates of incident STIs, adjusting for testing frequency given potential increased frequency among PrEP initiators.

9.2.3 Exploratory Outcomes Analyses

As exploratory analyses, we will also report the effectiveness of the intervention as measured by PrEP uptake at the 3-month follow-up stratified by sex. The effectiveness of the intervention will be estimated as the difference in proportion of women starting PrEP within 3 months of an index STI clinic visit, comparing randomized to the intervention and control groups. For participants enrolled through clinic-collaborating outreach events, the date of clinic outreach serves as the index visit.

9.2.4 Additional Outcome Analyses

Additional analyses will compare self-reported PrEP use among patients who complete the self-administered screening questions (Section 5.4) but who do not enroll in the study (ineligible or eligible but decline). Specifically, we will examine the proportion of respondents endorsing recent or current PrEP use and trends throughout the enrollment period to evaluate “background” PrEP use in the community of patients seeking STI services at participating clinics. We will estimate the proportion reporting PrEP use in each month as the number of patients reporting current PrEP use divided by the number of patients completing the screening questionnaire. We will compute trends in PrEP use by regressing these estimated monthly proportions on time using logistic regression and interpreting the regression coefficient on time.

We will also explore effective-PrEP use, namely PrEP use that aligns with periods of HIV risk^{50,51} using daily app data of tracked sexual behaviors, incident STIs, and PrEP use for persons in the intervention arm. As the daily tracking feature is only in the intervention arm app, this outcome will be exploratory for use in future work.

Additional exploratory analyses will examine PrEP uptake, persistent use, HIV or STI incidence, and intervention satisfaction/preferences at 12-months. All measures will be self-reported and captured using CASI. Only persons who reach the 12-month follow-up visit within the allowable data collection window will have these assessments completed.

We will examine whether there are subgroups (of clients and/or clinics) for which the intervention may be more or less effective (see Section 11.0).

We will also examine the proportion starting PrEP separately for patients enrolled in each calendar year quarter of the study to explore trends over time.

This assessment describes process indicators to inform intervention implementation, optimization, and scale-up. We will measure acceptability of the implementation strategies to providers and clinic directors, feasibility of the intervention, and intervention satisfaction among patients and providers.

To measure acceptability of the intervention and to explore clinic-level influences on implementation feasibility at each clinic, we will interview providers and clinic directors. We will assess factors such as provider burden of intervention, adequacy and timing of training, supervision/support structure, organizational readiness for change (quantitative scale and qualitative interviews),³⁹ management support (qualitative interviews), implementation climate (quantitative scale and qualitative interviews),⁴⁰ and intervention-values fit (quantitative scale and qualitative interviews)⁴¹. We will use facility audit data, including county population, patient panel size and demographics, number and training level of clinic staff, clinic staff-to-patient ratio, daily patient volume, open hours and local access to PrEP to contextualize determinants.

Feasibility measures will assess patient engagement with the intervention, including uptake of elements (i.e. linkage to insurance if not durably insured at enrollment, use of telehealth PrEP, interactions with PrEP navigators). We will examine the percent of enrolled participants in the intervention arm who are engaged by the PrEP navigator within two weeks of enrollment. We will also examine app-specific engagement, including successful app installation, account creation and log-in, total number of log ins, and time spent in the app.

Measurement of patient satisfaction with intervention includes qualitative (IDI data) and quantitative (e.g. System Usability Scale) assessments. We will conduct interviews with a subset of patients regarding their experiences with the intervention. This sample will include a mix of persons with variable HMP engagement and PrEP uptake. We will ask about satisfaction with clinician interactions, time and financial cost, and perceived quality of PrEP care. As a quantitative assessment, all participants will complete a satisfaction scale at quarterly follow-up visits⁵².

Analysis of implementation outcome measures will include qualitative analysis. Interviews will be recorded and transcribed. Transcripts from participants and providers/clinic staff will be analyzed separately and reviewed for quality.

Interview transcripts will be thematically analyzed following a combination of deductive and inductive analytic approaches. An initial codebook will be developed based on *a priori* concepts driven by the theoretical underpinnings used to develop the interview guide. All textual data will then be read thoroughly to summarize first impressions. Emerging themes will be incorporated into the codebook. Pre-existing codes may be modified based on interview transcripts. Transcripts will be coded iteratively using qualitative analysis software. Two

researchers will code interviews separately to assess inter-coder reliability. The codebook will be revised and updated. Analysis of the coded data will include investigation of relationships between codes, coding matrices, and mapping of codes and themes. Data from qualitative interviews will be triangulated with the quantitative data to gain a more complete understanding of the factors underlying implementation. For example, if our survey data show that clinics with lower fidelity tended to score low on the implementation climate scale, we will examine our qualitative data for indications about what aspects of the leadership or climate may have contributed.

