Among NC counties with the most HIV diagnoses in 2019, four have rural designation and nine are small or medium metropolitan areas^{7,11}. The lack of robust healthcare infrastructure in these areas presents challenges for HIV prevention services. NC's HIV epidemic tracks alongside rising sexually transmitted infections (STI)¹² with disproportionately high burden among rural YSGM. **Despite behavioral risk overlap of incident STIs/HIV, in NC, PrEP is only offered at a few, primarily urban health department (HD) affiliated STI clinics^{13,14}.** As of November 2022, we have identified 15 HD-affiliated STI clinics in relatively high-HIV burden, rural (n=13) or peri-urban (n=2) counties across NC who are interested in participating in this study. As of January 2024, the study is expanding to additional rural and peri-urban STI clinics in NC. All patients who are seeking STI testing at the participating clinics are offered HIV testing on-site. Per NC standard of care, all patients who are diagnosed with HIV are referred to immediate ART care, which may be offered onsite or through other HIV providers. However, **linkage to PrEP services is not well-established: at the initial 15 participating HD STI clinics, as of May 2023, one clinic (Wilson County, rural) offers referral to a co-located primary care clinic that can prescribe PrEP. The remaining 14 HD clinics do not provide any PrEP services to patients beyond passive referral to services in the community (e.g. patient is provided private practice provider name(s) that may offer PrEP services. None of these 15 clinics have providers "in-house" prescribing PrEP and none have PrEP navigation services.** STI clinics are a logical entrée to PrEP, but ineffective integration in rural HDs reflects heterogeneity in clinic structure and staffing: STI clinics are designed to provide episodic care, whereas PrEP services require additional human resources and longitudinal engagement to be effective¹⁵. Leveraging STI clinics as an on-ramp to PrEP is a compelling opportunity to capitalize on STI service encounters and address disparities in PrEP access for YSGM¹⁶⁻¹⁸.

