9.0 STATISTICAL/ANALYTIC CONSIDERATIONS

9.1 Sample Size and Power Estimate

We expect > 7,400 patients will present for care in the 21-month enrollment period, with 20-35% study eligible. Aim 1 analysis includes eligible, consenting patients who successfully download the HMP app. The study will enroll for 21 months with a target sample size of 336. We expect approximately half of participants will be randomly assigned to the intervention arm and the remaining half to the control arm (see Randomization, Section 3.2).

We calculated statistical power for the effect of intervention upon PrEP uptake by 3-month follow-up using SAS 9.4 (Cary, NC) with a 5% type I error rate and a two-sided Chi-square test. Assuming 2.5% of eligible patients start PrEP within 3 months in the control arm, we calculated statistical power to detect a range of small to large effect sizes from 5% to 15% percentage point increases in PrEP uptake under a range of possible sample sizes and assuming 10% missing data (Table 4). At a total sample size of 336, given our design and assumptions, we will have >88% statistical power to detect medium (10%) and large (15%) effect sizes, and 80% statistical power to detect a moderate (7.5%) effect size.

Effect size rationale: As there is currently limited-to-no infrastructure or existing programming providing PrEP in rural North Carolina STI clinics, no prior studies that we are aware of have measured PrEP uptake in these settings. Overall, U.S. PrEP coverage of those assigned male sex at birth with PrEP indications was reported by CDC as 18.4% in January – March 2021, but only 5.6% among Black/African American⁴⁶, who will constitute a large portion of our sample. Among the CDC-designated End-the-Epidemic jurisdictions, recent PrEP coverage estimates of those with PrEP indications range from a low of 4.5% in San Bernardino to a high of 42.3% in San Francisco; North Carolina's state level PrEP coverage estimate is 13.3%, which belies the wide variability from

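### The background PrEP trend in Section 9.2.4 has no site term although the site set changes in 2024, and does not say how monthly denominators enter the model

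*Combined protocol and SAP*

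**What the plan says.** Section 9.2.4 plans to describe background PrEP use among people who complete the screener "but who do not enroll in the study (ineligible or eligible but decline". The monthly estimate is the "number of patients reporting current PrEP use divided by the number of patients completing the screening questionnaire". The trend comes from "regressing these estimated monthly proportions on time using logistic regression", and the coefficient on time is what will be interpreted. No weights, variance estimator or covariates are named. The same paragraph first speaks of recent or current use, then of current use only.

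The site set is not constant. Section 1.0 says: "As of January 2024, the study is expanding to additional rural and peri-urban STI clinics in NC". Section 3.1 describes the sites added from 2024 as lying in urban and peri-urban counties, and says that 13 of the 15 counties participating in December 2023 were rural. The two sections differ on whether the additions are rural or urban; under either, the set changes during enrollment. Section 5.2 gives each county its own QR code, so every completed screener is tied to a county.

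**The concern.** The plan interprets one coefficient on calendar time. If added sites have a different level of PrEP use from the original ones, the pooled proportion shifts when they join, and a model with time as its only term reads that shift as a trend. Section 9.1 itself remarks on wide urban-to-rural variability in PrEP coverage, so a difference is plausible.

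The second issue is how the proportions enter the model. A logistic fit with one row per month and no denominator treats a month with 15 screeners and a month with 80 as one observation each. Its model-based standard error does not shrink as screeners accumulate.

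At stake is the credibility of a contextual result. A spurious rise or a missed rise would mislead anyone using it to judge how PrEP use was changing around the trial.

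**Working it through.** The plan gives no precision or power for this trend, so there is no figure to reproduce.

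**Inputs from the documents**
- Length and enrollment: "The study will enroll for 21 months with a target sample size of 336", so 336/21 = 16 enrolled per month.
- Ceiling on screeners: "We expect > 7,400 patients will present for care in the 21-month enrollment period", so 7,400/21 ≈ 352 per month if every patient completed the screener. Expected completions are not stated.
- Coverage figures in Section 9.1: 5.6% (Black/African American), 13.3% (North Carolina), 18.4% (national, assigned male at birth).
- Timing: Table 6 has enrollment beginning by grant month 12, and Year 1 ends 31 May 2023. January 2024 then falls about 7 months into enrollment. The actual start date is not given.

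**Assumptions**: monthly screener counts, PrEP use in each site group, and the month of expansion. The coverage figures stand in for use among screeners, which the documents do not report.

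**1. Site mix.** Months are numbered 0 to 20. Original sites have 50 screeners per month at a flat 5.6%. Added sites contribute another 50 per month from month 7, also flat. The pooled proportion moves from 5.6% to the average of the two groups, for example (5.6 + 13.3)/2 = 9.45%. Each fit used events/trials, so denominators were handled correctly (500 replicates, two-sided 5% test).

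| Use at added sites | OR per month, time only | OR over 20 months | False-positive rate | With site term: OR per month, false-positive rate |
|---|---|---|---|---|
| 10% | 1.018 | 1.43 | 16% | 1.00, 5% |
| 13.3% | 1.027 | 1.71 | 39% | 1.00, 4% |
| 18.4% | 1.038 | 2.10 | 75% | 1.00, 5% |

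Correct weighting alone does not remove the spurious trend.

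**2. Denominators.** With m screeners in every month, proportion p and no trend, the grouped-fit slope has SE = 1/√(m·p(1−p)·Σ(t−t̄)²). For 21 months Σ(t−t̄)² = 21 × (21² − 1)/12 = 770. At p = 0.133, p(1−p) = 0.1153.
- Unweighted with model-based SE (m = 1 in the formula): 1/√(0.1153 × 770) = 0.106, whatever the true count. Simulation gave 0.106 to 0.108.
- Grouped: 0.106/√16 = 0.027 at 16 per month; 0.106/√100 = 0.011 at 100.
- The ratio is √m: 4.0 at 16, 5.5 at 30, 7.1 at 50, 10 at 100, 18.8 at 352.

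With 15 screeners per month for 7 months and then 80, and a true slope of 0.04 on the logit scale, that unweighted fit detected the trend in 0% of replicates and the grouped fit in 77%.

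**3. How far this depends on the variance method.** The same unweighted proportions gave SEs of 0.97 to 1.06 times the grouped SE with quasi-binomial scaling, and 0.88 to 1.11 times with robust SEs. Robust SEs had false-positive rates of about 9% to 11% with 21 points. What remains is lost efficiency when months are unequal: the true SD of the slope was 0.0213 against 0.0176 (ratio 1.21) with no trend, and 0.0197 against 0.0151 (ratio 1.30) with slope 0.04.

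**4. Population.** Assume 50 completers in a month, 5 of them current users. Over all completers use is 5/50 = 10%. Over non-enrollees it is 5/34 = 14.7% if 16 enroll and 5/42 = 11.9% if 8 enroll. Current users cannot enroll (Section 5.1), so a non-enrollee denominator would move with enrollment pace even if use were flat.

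**The case against.** A reader might infer that the plan ignores monthly denominators, makes its error bars several-fold too wide and could almost never detect a trend. The documents do not support that as fact. Section 9.2.4 defines both counts, and a logistic fit of a proportion with its denominator is a standard reading of the sentence. The severe widening needs an unweighted fit together with model-based SEs, and the plan prescribes neither. What stands is that the text does not say which fit is meant, and the readings differ several-fold in SE.

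A reader might also infer that this is the trial's only gauge of background PrEP use, or that it corrects the Phase 2 comparison with R61 controls. It is neither. Table 6, footnote c, gives the concurrent control arm the role of showing background uptake, and Section 9.2.4 also plans PrEP starts by calendar quarter. Section 13.3 deals with temporal trends in Phase 2 without using the screener trend.

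The complaint that users are over-represented largely dissolves, because the stated formula divides by all questionnaire completers. Only the introductory restriction to non-enrollees conflicts with it.

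On site mix, the stated target is use among patients at participating clinics, so a change of clinics is arguably part of the description. That is fair for a monthly table, less so for a coefficient interpreted as a trend over time. It is also true that no screener data show that original and added sites differ, and that a full county term may be unstable: at 10 screeners per month and 10% use there are 21 × 10 × 0.10 = 21 events, about 1.4 per county over 15 counties.

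**Conclusion.** The point holds as an omission with a definite consequence. The time coefficient is entangled with the 2024 site expansion, and neither the use of denominators nor the variance method is stated. The bias is conditional on background use differing between original and added sites; under the assumed inputs it is an odds ratio of about 1.02 to 1.04 per month with false-positive rates of 16% to 75%. If the two groups have the same level of use, this bias does not arise. The √m widening is a risk of one implementation; with a sound variance estimator the cost of ignoring unequal denominators is a slope SD about 20% to 30% larger. Every magnitude rests on assumed screener volumes and levels of use. The impact is low, because no primary, secondary or Go/No-Go result depends on this analysis.

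**What to change.** In Section 9.2.4, specify logistic regression on individual screener records, or on events/trials by month and county, for all non-duplicate screener completers. Include an original-versus-added-site term, or county where the number of events allows. State the variance method, including any allowance for overdispersion or clustering by county. Report the trend restricted to the initial 15 counties as a check. Choose one numerator, either current use or recent-or-current use, and one population, and use them throughout the paragraph.

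The cost is a few sentences, since screener responses and county are already collected. The downside is some loss of precision from the site term when events are few, which is why a two-level site term is the safer default over 15 or more county terms.

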3.1 Collaborating STI Clinics

In coordination with North Carolina DHHS partners, we utilized county-level 2019-2021 HIV/STI data (reported to the State Laboratory of Public Health [SLPH]), to identify local Health Department STI clinics for participation. Specifically, we examined testing volume and test positivity rates by reported race/ethnicity among men <40 years of age. We also used National Center for Health Statistics urban-rural classification scheme, limiting to counties designated as small (<250,000) or medium (<1,000,000) metropolitan counties, and nonmetropolitan (rural) counties including micropolitan counties (counties associated with at least one urban cluster $\geq 10,000$ but $\leq 50,000$ population) and non-core counties (nonmetropolitan counties that are not in a micropolitan statistical area)³⁴. Starting in 2024, additional organizations that offer STI services and which are located in urban and peri-urban designated counties in NC will be identified as part of the recruitment expansion strategy. Throughout the protocol, locations where STI services are offered are referred to as “clinics” or “STI clinics”, however these locations may also include non-traditional modes of delivering STI services, for example, mobile van clinics, services housed within community-based organizations, and clinic-affiliated health fairs or other events.

All eligible clinics are contacted with information about the study and an invitation to participate. The study team meets with clinics to assess interest and appropriate fit. Clinics that decide to participate provide signed Letters of Support indicating commitment to collaborate, as well as roles and responsibilities.

Of the 15 participating counties participating in the study as of December 2023, 13 are designated as rural³⁴.

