5.2 Participant Recruitment

The study team and clinic representatives will meet as needed to troubleshoot any clinic-specific or cross-clinic recruitment challenges, as well as share successes.

Venue-based recruitment at participating STI clinics: Ads (e.g. posters, one-pagers) and business cards/palm cards with scannable QR codes will be posted throughout the clinic waiting areas, bulletin boards, patient rooms, etc. The study will also be promoted through word of mouth via the clinic health professionals, administrative staff, and community outreach personnel. Clinic and study staff may also bring recruitment materials to community-based events they attend on behalf of the clinic (e.g. health fairs, blood drive) with information about the study and encouraging persons to seek STI services at their local STI clinic.

Primary recruitment materials: Scannable QR codes will lead to a study landing page and online screener, which allows people to learn about the study discretely if they do not wish to carry study-related materials on their person. Each county will be assigned an individualized QR code so that study staff can recognize which county each completed screener is associated with. If multiple collaborating clinics exist within one county, the participant will self-report from which clinic they engaged with recruitment materials. We will work with clinic staff and our Community Advisory Board to develop a comprehensive recruitment portfolio, reviewing messages, imagery, tone and dissemination modalities. All recruitment materials will be reviewed and approved by the IRB prior to use.

Social media promotion: In addition to clinic-based recruitment, we will also work with each clinic to establish a social media recruitment plan. To maintain consistency across clinics, the intention of the social media promotion is to increase visibility of the clinic to the target population and encourage our population of interest to seek sexual health services through the collaborating clinics.

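### The background PrEP-use trend is fitted on time alone, so counties added from 2024 can move the slope with no change in PrEP use inside any county

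*Combined protocol and SAP*

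**What the plan says.** Section 9.2.4 uses the screening questionnaire to describe PrEP use "in the community of patients seeking STI services at participating clinics". Each month's figure is "the number of patients reporting current PrEP use divided by the number of patients completing the screening questionnaire". The trend then comes from "regressing these estimated monthly proportions on time using logistic regression and interpreting the regression coefficient on time". No county, clinic or site-entry term is named. No test, significance level or decision rule is attached.

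The set of sites changes over the study. Section 1.0 describes 15 initial health department clinics "in relatively high-HIV burden, rural (n=13) or peri-urban (n=2) counties across NC", and continues: "As of January 2024, the study is expanding to additional rural and peri-urban STI clinics in NC". Section 3.1 describes the expansion differently: "Starting in 2024, additional organizations that offer STI services and which are located in urban and peri-urban designated counties in NC" are to be identified. Section 9.1 remarks that North Carolina's statewide PrEP coverage of 13.3% hides wide variation between urban and rural areas.

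County is known for every screener. Section 5.2 states: "Each county will be assigned an individualized QR code so that study staff can recognize which county each completed screener is associated with".

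**The concern.** The series is meant to show whether PrEP use among patients at participating clinics changed during enrolment. A pooled monthly proportion is an average of county levels, weighted by how many people each county screened that month. It can rise because use rose within counties, or because counties with higher use joined. A model with time as its only regressor cannot separate the two.

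The plan supplies most of the ingredients for the second explanation: sites are added, section 3.1 puts them in more urban counties than the initial mainly rural set, and coverage is said to vary along that axis. It does not show that added counties have higher use among screeners.

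What is at stake is the interpretation of one descriptive result. A slope produced by opening new sites could be reported as rising use in the community or, if the added counties had lower use, as falling use.

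**Working it through.** The plan states no standard error, power or sample size for this trend, so there is no figure to reproduce. The check asks what the time-only model returns when PrEP use is constant within every county.

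**Inputs from the documents**
- Enrolment lasts 21 months (section 9.1).
- Volume: "We expect > 7,400 patients will present for care in the 21-month enrollment period, with 20-35% study eligible". The eligible number is 7,400 × 0.20 = 1,480 to 7,400 × 0.35 = 2,590. Screener completers are not stated, so these two totals serve as illustrative sizes.
- 5.6% and 13.3% are coverage levels quoted in section 9.1: the national figure for Black/African American people with PrEP indications, and the statewide figure. Neither describes screeners or particular counties. They are borrowed only as plausible levels.

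**Assumptions**
- The low-volume case is 20 screeners per month, 20 × 21 = 420.
- Added counties enter at month 7, 8 or 11. No enrolment start date is given. Table 6 has enrolment beginning by the end of Year 1 (May 2023). A June 2023 start would make January 2024 month 8.
- Added counties supply half of screeners after entry, or a quarter as a milder case.

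**Step 1: effect on the pooled proportion.**
- Before expansion it is 5.6%.
- After it, 0.5 × 5.6% + 0.5 × 13.3% = 9.45%.
- The odds go from 0.056/0.944 = 0.0593 to 0.0945/0.9055 = 0.1044, a ratio of 1.76, with no change in any county.

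**Step 2: slope from the time-only model.** The model is logit(p_m) = a + b × (m/12), fitted to expected counts with the monthly denominators included. The true within-county odds ratio is 1.00 throughout.

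| Use, initial vs added | Entry and share | Odds ratio per year |
|---|---|---|
| 5.6% vs 13.3% | month 7, half at once | 1.43 |
| 5.6% vs 13.3% | month 8, rising to half by month 14 | 1.58 |
| 5.6% vs 13.3% | month 11, half at once | 1.61 |
| 5.6% vs 13.3% | month 8, rising to a quarter | 1.29 |
| 10% vs 13.3% | month 7, 8 or 11, half | 1.12 to 1.16 |
| equal | any | 1.00 |
| 13.3% vs 5.6% | month 8, rising to half | 0.73 |

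The last row reverses the gap, to show that the sign depends on which counties have higher use.

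**Step 3: how often the slope would look real.** Counts were simulated with 5.6% versus 13.3%, entry from month 8 and a share rising to half. The measure is how often |z| exceeds 1.96, that is, how often a 95% interval excludes no trend. It is only a gauge, since the plan declares no test.
- With two county groups (2,000 series), the time-only model exceeds the limit in 63% of series at 1,480 screeners and 88% at 2,590. With a county-group term the figures are 5.0% and 4.2%.
- With a separate fixed effect for each of 15 initial and 10 added counties (10 is an assumption; 400 series), the time-only model gives 21%, 60% and 87% at 420, 1,480 and 2,590 screeners. The county-adjusted model gives 8%, 5% and 5%.

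**Step 4: price of the adjustment.** In the month-8 scenario at 1,480 screeners, the standard error of the yearly log odds ratio rises from 0.197 to 0.239 with a county-group term, a factor of 0.239/0.197 = 1.21. With equal use in both groups (8%), it rises from 0.190 to 0.216, a factor of 1.14.

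**The case against.** The strongest reply is that this is a descriptive, additional analysis. No milestone in Table 6 uses it. The randomised comparison has a concurrent control arm and is stratified by county. Section 13.3 handles temporal change in the later phase by looking at uptake over time and does not draw on the screener series. All of this stands and sets the severity.

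Section 1.0 describes the added clinics as rural and peri-urban, the same types as the first 15, which gives no reason to expect different use. Section 3.1, however, says urban and peri-urban, so the plan does not settle the matter. The size rests on assumed counts, shares and levels. That also stands: the bias vanishes if counties are alike.

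A fixed effect for every county could be unstable with few screeners. At 420 screeners, 15 counties would average 420/15 = 28 each, or about 28 × 0.056 = 1.6 users. The check shows mild strain at that size (8%) and none at 1,480 or more. Grouping small counties answers it.

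A reader might infer more than the documents support:
- **That the standard error ignores how many people were screened.** Section 9.2.4 names both the monthly numerator and the denominator, and an ordinary logistic fit to events out of trials uses both. Only an unusual reading, one trial per month, discards them.
- **That a hypothesis test is invalid.** None is declared.
- **That counties leave the series.** The documents show only additions.
- **That the calendar-quarter description of PrEP starts has the same fault.** No regression is specified there.

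**Conclusion.** The point holds as a low-severity one. As written, the time coefficient answers a question about the changing pool of screeners, not about change within the communities served. Under the illustrative case (5.6% versus 13.3%, half of later screeners from added counties) the spurious odds ratio is about 1.5 per year, ranging from 1.43 to 1.61 with the timing of entry. It is 1.29 if added counties supply a quarter of screeners, and close to none if the counties are alike. These sizes rest on a true difference in use between initial and added counties and on expansion falling inside the 21 months. The first cannot be confirmed from the documents; the second is likely but not stated. The randomised primary comparison does not depend on this analysis.

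**What to change.** Replace the trend sentence in section 9.2.4 with wording such as:

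> The trend in current PrEP use will be estimated by logistic regression on individual screener records (current use, yes or no), with calendar month as the exposure and county, taken from the QR code, as a fixed effect. Counties with few screeners will be grouped by a rule set before the data are examined. The odds ratio per month will be reported with its 95% confidence interval, beside the pooled trend and the estimate restricted to counties open throughout enrolment.

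If aggregate data are preferred, events out of trials by county and month give the same model.

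The cost is a wording change. County is already recorded, and the monthly counts the plan uses already require the screening date, so no new data are needed. The interval widens somewhat: by 14% when county use is in fact equal and by 21% in the main illustration. Keeping the pooled trend in the report preserves the description of overall use among everyone screened.
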